## 2.4. Protocol Deviations/Violations

Protocol deviations and violations will be summarized outside of this statistical analysis plan.

## 2.5. Study Day

Study day is defined as:

- Event Date – First Dose Date + 1 if the event date is on or after the first dose date
- Event Date – First Dose Date if the event date is before the first dose date

Study Day 1 is defined as the first dose date.

## 2.6. Study Endpoint Baseline

When required for the statistical analysis of a variable, the baseline value will be the last recorded value prior to randomization. The exceptions are the baseline 24-hour UPE, 24-hour uPCR, and 24-hour uACR, which are defined as the average of the two respective pre-dose values collected during the last two weeks of the Run-In Period before randomization.

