10.1.6. Randomization

Patients may be randomized at the time of the Treatment 1 Visit (T1) or up to 24 hours prior to T1. Eligible patients will be randomized in the study via an electronic randomization system. Patients will be randomized in a ratio of 1:1 double-blind assignments to narsoplimab (active

CONFIDENTIAL

No use, disclosure, or reproduction outside of Omertos without prior written authorization

treatment group) or placebo group. Randomization will be stratified by the baseline eGFR level (≥ 30 to ≤ 45 mL/min/1.73 m² and > 45 mL/min/1.73 m²) and by baseline UPE (> 1 to < 2 g/day and ≥ 2 g/day).

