Data collected at the final Run-In Visit will serve as the study baseline. After completion of this period, patients who are eligible and who enroll in the Initial Treatment Period will be randomized in a double-blind manner into one of two groups: the placebo or active (narsoplimab) treatment group.

CONFIDENTIAL

No use, disclosure, or reproduction outside of Omersa without prior written authorization

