10.2.3.2. Treatment Visit 1 (T1, Week 1)

Treatment Visit 1 should be scheduled to occur as soon as possible from receipt of all laboratory results, and no more than 7 days from receipt of all laboratory results, including the second 24-hour UPE result from the final RI visit.

During T1, the procedures listed below will be performed and documented prior to treatment with study drug:

- Perform randomization in the electronic randomization system (if not previously completed in the 24 hours prior to the visit) (this procedure will not be repeated for patients who resume or reinitiate study treatment after a COVID-19 related interruption)
- Collect vital signs including BP, pulse rate, RR, and temperature (all after at least 5 minutes in a seated position)
- Complete pre-dose ECG after patient has been supine for at least 5 minutes
- Collect urine sample and complete pregnancy test
- Assess AEs
- Assess concomitant medications/therapies
- Confirm and document ongoing use of medically acceptable birth control method for patients of childbearing or reproductive potential
- Confirm and document stability of RAS blockade

The study drug should be prepared and infused per Section 9.4.

CONFIDENTIAL

No use, disclosure, or reproduction outside of Omersus without prior written authorization

During T1, the procedures listed below will be performed and documented following treatment with study drug:

- Collect vital signs including BP, pulse rate, RR, and temperature (after at least 5 minutes in a seated position) approximately 5 minutes after the end of the study drug infusion and 30 minutes (\pm 5 minutes) after the end of the study drug infusion
- Complete post-dose ECG at the end of the study drug infusion after at least 5 minutes of rest in a supine position; this should be obtained immediately before the post-dose PK/PD samples
- Collect PK/PD samples 15 minutes (\pm 5 minutes) after the end of the study drug infusion

At site discretion and for patient convenience, dispense 24-hour urine collection supplies to the patient at any time during T1 to T10 along with collection instructions. Patients will have the option to collect the 24-hour urine specimen at any point between T10 to T11. Patients should be instructed to return the 24-hour urine specimen to the clinic as soon as possible following its collection.

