10.2.11. Timing of Study Procedures

Procedures with a specified time frame will be considered per protocol if they are performed within the following windows: vital signs and ECGs on dosing days prior to drug administration; vital signs on dosing days after the end of the study drug infusion \pm 5 minutes and 30 minutes after end of IP infusion \pm 5 minutes; PK/PD draw at T1 \pm 5 minutes; PK/PD draw at T2 (168 hours after the start of the first dose) \pm 2 hours. If multiple procedures are specified at one timepoint, they should be performed in the following order: vital signs, ECG, and then blood draw.

CONFIDENTIAL

No use, disclosure, or reproduction outside of Omertos without prior written authorization

At site discretion and for the convenience of the patient, the 24-hour urine collection supplies may be dispensed to the patient at any time during the applicable study periods (Run-In Period, Extended Treatment Period, Response Evaluation Period, Relapse Retreatment Period, Open Label Treatment, and Follow-Up Period) along with collection instructions. Patients should be instructed to return the 24-hour urine specimen to the site as soon as possible after its collection.

During the Run-In Period, two 24-hour urine samples will be collected no more than 14 days apart during the last 2 weeks of the Run-In Period. During the Response Evaluation Period, to assess patient response and potential need for relapse retreatment, a 24-hour UPE will be performed at the Week 24 timepoint and again at the Week 30 timepoint. Patients will be required to collect one 24-hour urine specimen at each timepoint. To provide flexibility for patients, each 24-hour urine may be collected within 7 days prior to or after each designated timepoint (Week 24 and Week 30).

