¹⁵ Vital signs: to be collected prior to dosing, approximately 5 minutes after the end of the 30-minute study drug infusion, and 30 minutes (\pm 5 minutes) following the end of the study drug infusion on study drug treatment days. During the COVID-19 pandemic: For study visits conducted virtually, it may be necessary for patient to collect his or her own pulse, systolic and diastolic BP, and body temperature. Patients will record pulse, systolic and diastolic BP and temperature on a patient diary and provide this diary to the study site. In the case of a thermometer shortage due to the COVID-19 pandemic, sites may allow a patient to collect body temperature with the patient's own thermometer.

¹⁶ During the Run-In visits, these assessments will only be performed if the patient is on stable BP medication and the visit is considered the final Run-In visit

¹⁷ During the Initial Treatment Period ECGs will be collected: pre-dose and at the end of the 30-minute infusion at T1 (to be obtained immediately before the 15-minute post-dose PK/PD samples), and pre-dose at T12

¹⁸ Patients should be instructed to return the 24-hour urine sample to the clinic as soon as possible following its collection. With patient consent, the 24-hour urine collection samples may be delivered from the patient's location to the study site or the central lab by a specialty courier selected by the sponsor.

¹⁹ Due to COVID-19 restrictions, it may be allowable for a local commercial laboratory to assess 24-hour UPE, uPCR, and uACR if neither the study site nor the local commercial lab is able to process and prepare the samples for delivery to the central lab. In this case only, the local commercial lab may assess 24-hour UPE, uPCR and uACR.

²⁰ To be done either before, during, or after T11

²¹ During the COVID-19 pandemic, it may be allowable for CMP, CBC+diff, HgbA1c, UA, uACR, and uPCR to be performed by a local commercial laboratory in cases where the patient is unable to travel to the study site or the study site is unable to receive or process the samples for delivery to the central laboratory.

²² During the Initial Treatment Period between T2 and T11, collection of the following laboratory samples occurs only at T4 and T8: blood for CMP, CBC + diff., spot urine for uPCR, uACR, and UA.

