### **3.4.4. Electrocardiogram**

The ECG parameters (heart rate, PR interval, QRS interval, QT interval, and QTc interval) at each time point as well as the change from baseline will be summarized with descriptive statistics by treatment period, treatment group, and scheduled visit. These parameters will be determined electronically by the ECG machine at the clinical site. QTc interval will be calculated using Fridericia's formula and will be categorized into the following groups:  $\leq 450$ ,  $> 450 - 480$ ,  $> 480 - 500$  and  $> 500$  ms. Categorized QTc interval will be summarized with frequency and percentage by treatment period, treatment group, and scheduled visit. Shift tables comparing the baseline categorized QTc interval to the maximum post-baseline categorized QTc interval will be provided by treatment period and treatment group. In addition, increase of  $> 30$  ms and  $> 60$  ms from baseline in QTc interval will be summarized with frequency and percentage by treatment period, treatment group, and scheduled visit.

The overall ECG assessment will be reported as "Normal," or "Abnormal – not clinically significant" or "Abnormal – clinically significant" with respect to relevant abnormalities by the investigator. Shifts from the baseline ECG assessment to the worst post-baseline ECG assessment will be tabulated by treatment period and treatment group.

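### ECG and vital-sign baseline stops at randomization, so T1 pre-dose readings taken after it are not baseline, and the pre-dose ECG can enter the post-baseline shift tables

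*SAP*

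**What the plan says.** **Baseline rule.** SAP 2.6 and protocol 14.1.6 agree: "the baseline value will be the last recorded value prior to randomization". The only exceptions are the 24-hour urine measures (UPE, uPCR, uACR), which use the mean of two Run-In collections. There is none for ECG or vital signs. Protocol 10.2.2 adds: "Data collected at the final Run-In Visit will serve as the study baseline".

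**When randomization happens.** Protocol 10.1.6: "Patients may be randomized at the time of the Treatment 1 Visit (T1) or up to 24 hours prior to T1". In protocol 10.2.3.2 the pre-treatment list for T1 opens with randomization, unless it was done in the preceding 24 hours. Vital signs come next, and then: "Complete pre-dose ECG after patient has been supine for at least 5 minutes".

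**ECGs at T1.** The schedule of events (protocol 20.2.1) has two: "pre-dose and at the end of the 30-minute infusion at T1".

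**How ECGs are analysed.** SAP 3.4.4: "Shift tables comparing the baseline categorized QTc interval to the maximum post-baseline categorized QTc interval will be provided by treatment period and treatment group". It also plans shifts to the worst post-baseline overall ECG assessment. QTc increases above 30 ms and 60 ms are counted by treatment period, treatment group and scheduled visit. SAP 3.4.3 plans only by-visit values and changes for vital signs.

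**The concern.** A safety baseline normally ends at the first dose, so that everything before drug exposure is reference and everything after it is outcome. Here it ends at randomization, which can precede the first dose by up to a day, with an ECG and a set of vital signs in between. Two things follow.

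1. The reading best placed to serve as reference is set aside in favour of one from the final Run-In visit. Changes in QTc and blood pressure then include any drift between the two visits. The end-of-infusion ECG at T1 is compared with a Run-In ECG rather than with the one taken shortly before the infusion.
2. An ECG recorded before any study drug can supply a patient's maximum or worst post-baseline value, so a pre-drug abnormality could be tabulated as a shift in the blinded period. SAP 3.4.1 counts treatment-emergent adverse events from the first dose, so the same finding would not be treatment-emergent there.

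**Working it through.** No figure in the plan rests on this rule, so the check applies the definitions to the T1 readings.

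**Step 1: are the T1 pre-dose readings before or after randomization?**
- Randomized ahead of T1: after, for certain.
- Randomized at T1: after, if the order of the list in protocol 10.2.3.2 is followed. Nothing requires that order. The one rule on sequence, in protocol 10.2.11, says of procedures sharing a timepoint that "they should be performed in the following order: vital signs, ECG, and then blood draw"; it does not place randomization.

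For same-day patients, baseline therefore depends on whether the ECG was taken before or after the randomization system was used.

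**Step 2: what becomes baseline?** SAP 2.5 defines study day from dates, with Day 1 as the first dose date. The T1 pre-dose reading has event date equal to first dose date, so study day = 0 + 1 = 1. In SAP Table 2 that lies inside the Initial Treatment Visit 1 window (Days 1 to 4) and outside the final Run-In window (Days -20 to -1, target Day -7). Without an unscheduled reading in between, baseline for patients randomized first is the final Run-In value.

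**Step 3: where can the pre-dose reading then appear?**

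| Table | Can it enter as a post-baseline value? | Reason |
|---|---|---|
| Maximum post-baseline QTc category (SAP 3.4.4) | Yes | Post-baseline is undefined and no rule removes pre-dose readings |
| Worst post-baseline ECG assessment (SAP 3.4.4) | Yes | Same |
| QTc increases > 30 ms and > 60 ms by visit (SAP 3.4.4) | No, if the tie rule is applied | All T1 readings fall on target Day 1; SAP 2.7 takes the latest, the end-of-infusion ECG |
| Vital signs by visit (SAP 3.4.3) | No, if the tie rule is applied | The latest is the set taken 30 minutes after infusion; no maximum or worst-value analysis is planned |

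The last two rows still compute change from the Run-In value.

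**Step 4: scale.** On the core schedule there are six ECGs after randomization: T1 pre-dose, T1 end of infusion, T12, and Weeks 36, 48 and 96. Anchoring to the first dose leaves five, since the T1 pre-dose ECG becomes the baseline.

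The documents give no within-patient SD for QTc, so the following rests on an assumed SD s of 8 to 15 ms, independent normal readings and no drug effect. The chance that at least one of k later readings exceeds baseline by more than 30 ms is

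1 - ∫ φ(b) Φ(b + 30/s)^k db.

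| Assumed SD | k = 6 | k = 5 | Difference |
|---|---|---|---|
| 8 ms | 2.0% | 1.7% | 0.3 points |
| 10 ms | 7.4% | 6.5% | 0.9 points |
| 15 ms | 26.7% | 24.2% | 2.5 points |

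A simulation of 400,000 patients gives the same differences, with 2.4 points at 15 ms. This shows only how much one extra drug-free reading raises a maximum. The SAP plans no any-visit > 30 ms rate, so these are not errors in a planned table.

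**The case against.** **The baseline is a stated and consistent choice.** Both documents give the same rule, and several protocol sections name the final Run-In evaluations as baseline. This stands: preferring a pre-dose baseline improves on a clear rule and does not correct a contradiction. One loose end remains: if T1 readings are taken before same-day randomization, the last-value rule points to T1 while protocol 10.2.2 points to the final Run-In visit.

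**Drift should be limited.** Protocol 10.2.2 requires stable, maximally tolerated RAS blockade before randomization, and stability is confirmed at T1. This largely stands, although blood pressure medication optimization is still a listed procedure at the final Run-In visit.

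**Post-baseline need not include pre-dose readings.** SAP 3.4 reports by blinded and open-label treatment period, and a programmer might reasonably leave pre-dose ECGs out of the former. That is a fair reading, but the text does not require it. The missing definition is the gap.

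**Stronger readings to resist.** A reader might infer that drug-free vital signs are reported as post-baseline data, or that the pre-dose ECG inflates the > 30 ms counts. The documents do not support either: these are by-visit tables, and the tie rule selects a post-infusion reading at T1. Nor do they support saying that no T1 pre-dose reading can ever be baseline; for same-day randomization that rests on list order alone.

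**Conclusion.** The point holds in a limited form. For patients randomized before their T1 readings, ECG and vital-sign changes are measured from the final Run-In visit although a later drug-free reading exists. Nothing in the SAP keeps that T1 ECG out of the maximum-QTc and worst-assessment shift tables.

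The consequence is small. Safety analyses are descriptive (SAP 2.9.4), the T1 procedures are the same in both blinded arms, and efficacy and the definition of treatment-emergent events are unaffected. The expected result is noise in both arms rather than a difference between them.

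Two conditions matter. How many patients are affected depends on how often randomization preceded the T1 readings, which the documents do not tell. The statement that by-visit tables are free of pre-dose values assumes that the SAP 2.7 tie rule, worded for two equally spaced readings, is also used for the three vital-sign sets at T1.

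**What to change.** 1. In SAP 2.6 and protocol 14.1.6, define baseline for ECG and vital signs as the last non-missing value before the start of the first dose of study drug.
2. In the same places, define post-baseline for safety tables as after the start of the first dose. This aligns the ECG shift tables with the first-dose anchor for treatment-emergent events in SAP 3.4.1.
3. Add a matching exception wherever the protocol makes the final Run-In evaluations the baseline: the synopsis and sections 7.1, 10.2.2, 10.2.2.2 and 10.2.2.4.
4. Leave the urine-protein and laboratory baselines as they are. T1 has no chemistry or haematology draw, so a first-dose anchor would change little there.

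The cost is a few sentences of text and a simple programming change. No new assessment is needed, and because the T1 pre-dose values precede all study drug, using them puts no treatment effect into the baseline.

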## 2.7. Analysis Visits

Two sets of analysis visits will be used. The first set ([Table 2](#)) is derived from the regular scheduled visits regardless of additional treatments (extended treatment, relapse retreatment, re-initiation of treatment open-label treatment, and open-label relapse retreatment; see the schedule of events in the protocol). Longitudinal data analyses will be based on the regular scheduled visits and time will be calculated from Day 1, unless otherwise specified.

The second set is derived for the additional treatment scheduled visits ([Table 3](#)).

**Table 2: Analysis Visits for Regular Scheduled Visits**

Visit	Target Day [Week]	Visit Window (Days)
4-week Run-In		
Screening	-63 [-9]	< -48
Run-In Visit 1	-35 [-5]	-48 to -21
Run-In Visit 2	-7 [-1]	-20 to -1
12-week Run-In		
Screening	-119 [-17]	< -104
Run-In Visit 1	-91 [-13]	-104 to -77
Run-In Visit 2	-63 [-9]	-76 to -49
Run-In Visit 3	-35 [-5]	-48 to -21
Run-In Visit 4	-7 [-1]	-20 to -1
Initial Treatment Visit 1	1 [1]	1 to 4
Initial Treatment Visit 12	78 [12]	5 to 120
Week 24	162 [24]	121 to 183
Week 30	204 [30]	184 to 225
Week 36	246 [36]	226 to 288 [33.1 to 41wk]

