14.1.6. General Considerations

Summary statistics for continuous variables will include number of patients, mean, median, standard deviation, minimum, and maximum. For categorical variables, frequencies and percentages will be provided. When required for the statistical analysis of a particular variable, the baseline value will be the last recorded value prior to randomization. The exception is the baseline 24-hour UPE, uPCR and uACR, which are defined as the average of the two pre-dose values collected during the last two weeks of the Run-In Period before randomization. In addition, study week is defined from study Day 1 and will be determined by analysis visit windows which are defined approximately equally over adjacent scheduled visits. A study endpoint at a particular study week (e.g., 24-hour UPE at 36 weeks) is the value collected during that analysis visit window. All statistical tests will be performed at the two-sided significance level of 5%. All confidence intervals will be constructed at the two-sided 95% confidence level.

CONFIDENTIAL

No use, disclosure, or reproduction outside of Omertos without prior written authorization

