**Table 2: Analysis Visits for Regular Scheduled Visits (Continued)**

Visit	Target Day [Week]	Visit Window (Days)
Week 48	330 [48]	289 to 414 [41 to 60wk]
Week 72	498 [72]	415 to 582
Week 96	666 [96]	583 to 750
Week 120	834 [120]	751 to 918
Week 144	1002 [144]	919 to 1086

If there are 2 or more assessments in the same analysis visit, the closest one to the target day will be used in the analysis. If there are 2 assessments that are equally spaced from the target day, the latest one will be used in the analysis, unless otherwise specified.

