### 2.9.2. Efficacy Analyses

Unless otherwise specified, time will be calculated from Day 1.

**Table 2** will be used to determine the analysis values and the timepoints to be used in the analysis regardless of missed visits, extended treatment, or re-initiation of treatment.

The UPE primary efficacy endpoint in the high-risk proteinuria group is unaffected by the associated blinded SSRE and, hence, no special considerations apply to the analysis of UPE data pre and post the planned SSRE.

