The restricted maximum likelihood (REML) method in SAS PROC MIXED will be used to fit the model. The treatment difference in the rate of change in eGFR over 2 years will be estimated from the model along with its standard error, 2-sided confidence interval and p-value. The applicable alpha level will be 5% in a 2-sided test. Denoting time as **T**, the SAS code will be of the form;

```
PROC MIXED DATA=Y COVTEST CL;
  CLASS PATIENT RANDTRT STRAT1 STRAT2;
  MODEL Y = T RANDTRT RANDTRT*T STRAT1 STRAT2 STRAT1*STRAT2/ SOLUTION COVB;
  RANDOM INT T / TYPE=UN PATIENT SOLUTION G GCORR;

  ESTIMATE "INTERCEPT NAR"      INTERCEPT 1 RANDTRT 0 1           / CL ALPHA=0.05;
  ESTIMATE "INTERCEPT PCB"      INTERCEPT 1 RANDTRT 1 0           / CL ALPHA=0.05;
  ESTIMATE "INTERCEPT NAR v PCB" RANDTRT 1 -1 T 0 RANDTRT*T 0 / CL ALPHA=0.05;

  ESTIMATE "SLOPE NAR"          T 1 RANDTRT*T 0 1 / CL ALPHA=0.05;
  ESTIMATE "SLOPE PCB"          T 1 RANDTRT*T 1 0 / CL ALPHA=0.05;
  ESTIMATE "SLOPE NAR v PCB"    T 0 RANDTRT*T 1 -1 / CL ALPHA=0.05;

  ODS OUTPUT "ESTIMATES"=EST;
  ODS OUTPUT SOLUTIONF=F;
  TITLE "RANDOM CO-EFFICIENTS ANALYSIS TOTAL SLOPE EGFR";
RUN;
TITLE;
```

Sensitivity analyses for both key secondary efficacy eGFR endpoints will include:

- Jump to Placebo Multiple Imputation
- Tipping Point Multiple Imputation

- COVID-19

with these analyses executed in the same fashion as described for the primary UPE endpoint.

While prior FDA co-authored publications and supportive simulations demonstrate that the use of fixed weights as per [Cui, Hung and Wang \(1999\)](#) are necessary to avoid alpha inflation associated with the SSRE procedure, an exploratory analysis of eGFR will be performed using an unweighted test statistic for the rate of change in eGFR over 2 years in the high-risk proteinuria group as requested by FDA.

Given the limited eGFR data points during the first 12 weeks of the study, the presence of an early, acute effect on eGFR cannot be meaningfully assessed. Nevertheless, mean change eGFR data will be presented by treatment groups at all sampling timepoints during the 2-year follow-up study period.

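### SAP Table 2 has no analysis visit between Day 4 and Week 12, so the T4 and T8 spot uPCR/uACR values drop out of the by-visit model

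*SAP*

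**What the plan says.** - SAP 2.7, Table 2: Visit 1 covers Days 1 to 4. The next row, "Initial Treatment Visit 12", has target Day 78 and covers Days 5 to 120. Table 3 supplies weekly windows, but only for extended treatment and retreatment, not for T2 to T11.
- Selection rule (SAP 2.7, repeated in 2.8): "If there are 2 or more assessments in the same analysis visit, the closest one to the target day will be used in the analysis".
- Scope (SAP 2.7): "Longitudinal data analyses will be based on the regular scheduled visits and time will be calculated from Day 1, unless otherwise specified". SAP 2.9.2 adds that Table 2 "will be used to determine the analysis values and the timepoints to be used in the analysis regardless of missed visits".
- SAP 2.9.2.4: the repeated-measures model for log spot uPCR and uACR uses the regular scheduled visits as its categorical time variable.
- Protocol 14.1.6: study week is set by "analysis visit windows which are defined approximately equally over adjacent scheduled visits".
- Protocol 20.2.1, footnote on T2 to T11: "collection of the following laboratory samples occurs only at T4 and T8". These are chemistry, blood count, spot uPCR and uACR, and urinalysis. eGFR is part of the chemistry panel (Protocol Table 2). Vital signs are taken at every infusion (Protocol 10.1.7 and 10.2.3.3).
- SAP 2.9.2.3: "mean change eGFR data will be presented by treatment groups at all sampling timepoints".
- SAP 3.4.2 and 3.4.3: laboratory and vital-sign summaries are by scheduled visit, with no reference to Table 2.

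**The concern.** A window that opens on Day 5 and targets Day 78 absorbs ten weekly treatment visits and keeps one value. The protocol pays for two interim laboratory and spot-urine samples during the main exposure period, and the stated windowing rule then removes them from the model meant to describe proteinuria by visit. The rule also allows a sample taken four weeks early to appear as a Week 12 result. If the same windows were used for the safety tables, the by-arm course of laboratory values and vital signs between Day 4 and Week 12 would not be shown.

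**Working it through.** **Inputs.** Target days and windows come from SAP Table 2. Visit tolerances come from Protocol 10.2.12.1: T4, T8 and T12 within 2 days, T11 within 3. Nominal day of visit Tk = 7(k − 1) + 1. This gives T12 = 7 × 11 + 1 = 78 and Week 24 = 7 × 23 + 1 = 162, as in Table 2.

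**Step 1. Reproduce the plan's boundaries by the midpoint rule of Protocol 14.1.6.**

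| Adjacent targets | Midpoint | Window end in Table 2 |
|---|---|---|
| 78, 162 | 120 | 120 |
| 162, 204 | 183 | 183 |
| 204, 246 | 225 | 225 |
| 246, 330 | 288 | 288 |
| 330, 498 | 414 | 414 |
| 498, 666 | 582 | 582 |
| 1, 78 | 39.5 | 4 |

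The rule holds at every later boundary checked and fails only where the Visit 12 window opens. Midpoints would open it on Day 40 if T1 were the neighbour, or on Day 75 if T11 were ((71 + 78)/2 = 74.5). The Visit 1 end at Day 4 matches the T1/T2 midpoint, (1 + 8)/2 = 4.5. It looks as if weekly rows were intended and T2 to T11 were then folded into Visit 12.

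**Step 2. Place the scheduled visits.** T2 to T11 fall on Days 8, 15, 22, 29, 36, 43, 50, 57, 64 and 71, all inside Days 5 to 120.

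**Step 3. Apply the closest-to-target rule.**
- T12 on schedule: at most 2 days from Day 78.
- T11 at its latest (Day 74): 78 − 74 = 4 days.
- T8 at its latest (Day 52): 78 − 52 = 26 days.
- T4 at its latest (Day 24): 78 − 24 = 54 days.

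An on-schedule T12 always wins. Spot urine is taken at T4, T8 and T12, so 2 of 3 on-treatment values per patient leave the model.

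**Step 4. T12 missed.** The nearest remaining initial-treatment spot value is T8, nominally 78 − 50 = 28 days early, and it enters as Week 12. For a patient on extended treatment starting on Day 85, the ExT4 sample (Day 106) is also 28 days away. The tie rule would take that later value if additional-treatment samples may fill a Table 2 window.

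**Step 5. Midpoint windows with T4 and T8 rows.** (1 + 22)/2 = 11.5; (22 + 50)/2 = 36; (50 + 78)/2 = 64; (78 + 162)/2 = 120. This gives T4 Days 12 to 36, T8 Days 37 to 64 and T12 Days 65 to 120. The protocol tolerances (Days 20 to 24, 48 to 52 and 76 to 80) fit with room to spare.

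**Step 6. Check the 24-hour UPE.** The Week 12 collection is made between T10 and T11, nominally Days 64 to 71, and T10 may be 2 days early (Day 62). A Day 65 lower limit would move some of these into the T8 row. The new limits therefore should not be used for 24-hour UPE.

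**The case against.** The strongest reply is that Table 2 was built for 24-hour UPE, which has no collection between baseline and the T10 to T11 interval, and that for UPE the wide window does no harm. That stands. The spot-urine model is also supportive and outside type I error control (SAP 2.9.1). The parallel model text in SAP 2.9.2.3.2 refers to scheduled timepoints, which could be read as nominal visits, although it too sits under the 2.9.2 instruction to use Table 2.

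A reader might infer more than the documents support:

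- **That early safety data never reach a by-visit table.** SAP 3.4.2 and 3.4.3 do not cite Table 2, and T4, T8 and T2 to T11 are scheduled visits in the protocol. Pointing the other way, SAP 2.8 lists the one-value rule among general methods for summaries, and Table 2 has rows for Screening, Run-In Visits 1 and 3 and T1, where no 24-hour UPE is collected. The question is open. Never also fails when T12 is missed, because an earlier value then enters.
- **That early eGFR is lost.** SAP 2.9.2.3 specifically promises all sampling timepoints, and the slope model uses actual assessment day. What remains is that Table 2 has no matching row.
- **That infusion-related blood-pressure changes could be seen only in this gap.** The same readings are taken at T1, at T12 and at every extended-treatment and retreatment infusion.
- **That the tie rule keeps one of the three same-day vital-sign readings.** The protocol defines these as separate timepoints, so collapsing them is an assumption.

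**Conclusion.** The gap in Table 2 is real, departs from Protocol 14.1.6, and has a stated consequence for one analysis. T4 and T8 spot uPCR/uACR (2 of 3 on-treatment values) leave the by-visit repeated-measures model when T12 is on schedule, and a missed T12 is normally filled by a value about four weeks early. On schedule means timed from the first dose. After a COVID-19 re-initiation the visits are recalculated from the new T1 (Protocol 20.4.2.2) while SAP Day 1 stays at the first dose, so T12 may then lie far from Day 78.

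For laboratory tests and vital signs the loss is conditional on scheduled visit meaning the Table 2 visit. On that reading it would be 2 of 3 on-treatment laboratory draws and vital signs from 10 of 12 infusions. Early laboratory extremes would still appear in the out-of-range listings and the worst-grade shift tables (SAP 3.4.2). For eGFR, two parts of the SAP need reconciling. The Week 36 UPE primary analysis and the eGFR slope are not affected.

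**What to change.** 1. Add two rows to Table 2 for spot urine, laboratory tests and eGFR: T4 (target Day 22, about Days 12 to 36) and T8 (target Day 50, about Days 37 to 64). Set T12 (target Day 78) at about Days 65 to 120 for these parameters. A missed T12 then stays missing instead of being filled from T8.
2. Keep Days 5 to 120 for the 24-hour UPE collected between T10 and T11.
3. State in SAP 3.4.2 and 3.4.3 what scheduled visit means. For vital signs, say that tables use the nominal weekly visits and show the pre-dose, 5-minute and 30-minute timepoints separately.
4. Reconcile Table 2 with the eGFR display in SAP 2.9.2.3, so that the T4 and T8 values have a labelled place.

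The cost is one SAP table, a few sentences and minor programming. No new data are needed.
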